# **3 Study Design**

## **3.1 General Design**

Double blinded, randomized controlled trial. All patients who present for primary, unilateral tricompartment TKA will be screened for inclusion. Consecutive patients who meet preset inclusion and exclusion criteria will be recruited either on day of surgery or in the preoperative anesthesia clinic by one of the study investigators. Written consent will be obtained for study participation. Patients who participate will be randomized into one of two treatment arms: continuous ACB with IPACK block versus continuous ACB with sham subcutaneous saline injection. Randomization will be done using the website random.org's Coin Flipper, selecting the Susan B Anthony coin, and flipping 5 coins. Majority heads will be randomized to receive the IPACK block whereas majority tails will be randomized to receive the sham subcutaneous injection. See Attachment A for an example of this website.

CONFIDENTIAL

This material is the property of Ochsner Clinic Foundation. Do not disclose or use except as authorized in writing by the study sponsor

Only the regional anesthesiologist performing the block will know the randomization status. The study participants, outcome assessors/researchers, other anesthesia personnel, surgeons, physician assistants, and nurses will be blinded to the treatment arm. All patients will receive sedation with midazolam and/or fentanyl titrated to comfort during block procedures. Per our standard practice at Ochsner Medical Center, all patients will have either spinal or combined spinal-epidural anesthesia with mepivacaine 1.5% as the primary anesthetic during the surgery and sedation with propofol titrated to comfort. Also per our standard practice at Ochsner Medical Center, multimodal therapy will include ketamine 0.25mg/kg IV (up to 50mg) intraoperatively, dexamethasone 8mg IV intraoperatively, pregabalin 150mg PO preoperatively (adjusted to 75mg for age over 70) followed by 75mg nightly (or home gabapentin dose), acetaminophen 1000mg IV followed by 100mg PO every 6 hours postoperatively, and celecoxib 400mg PO on POD #0 followed by 200mg PO daily.

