### **3.2 Primary Study Endpoints**

- Cumulative opioid consumption (morphine equivalents) in the first 24 hours

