### **3.3 Secondary Study Endpoints**

- Patient satisfaction on day of discharge using the Brief Pain Inventory (BPI) or a similar validated satisfaction survey
- Average pain score at rest and with physical therapy in PACU, POD#1 am, POD#1 pm
- Worst pain score at rest and with physical therapy in PACU, POD#1 am, POD#1 pm
- Walk distance on POD#1 am, POD#1 pm, POD#2
- Time to first intravenous opioid, oral opioid in PACU and after arrival to hospital room
- Time to oral-only opioids
- Pain location
- Hospital length of stay
- Incidence of foot drop
- Incidence of itching, nausea, or vomiting in PACU, POD#1am, POD#1 pm
- Incidence of over-sedation based on Richmond Agitation Sedation (RASS) score

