## **6.2 Postoperative Course**

No further procedures are required.

At 24 hours, the cumulative opioid consumption will be summated. An outcomes assessor will survey the patient at pre-specified times for secondary outcomes. Additional secondary outcomes will be pulled from the electronic medical record.

Per standard of care at Ochsner Medical Center, patients that meet clinical milestones will be discharged home on the afternoon of POD#1 with an on-Q pain ball that will be removed by the patient after approximately 48 hours.

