## **7 Statistical Plan**

### **7.1 Sample Size Determination**

Prior published literature demonstrates analgesic equivalence between adductor canal block and femoral nerve block. An institutional retrospective study here showed a 38.8% effect difference between femoral nerve block with and without IPACK. Using this information, for an effect size of 0.4, power of 0.8, and significance level of 0.05 we determined a sample size of 64 patients. Assuming a dropout rate of 10%, we will include 72 patients in this study with approximately 36 patients per study arm.

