### **7.2 Statistical Methods**

A t-test will be used to compare the two arms of the study. We will apply other statistical methods as per Ochsner's statistics team & researchers.

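### Time to first opioid is split by route and location, with no time zero and no overall version, so its room and single-route components can favour a patient already treated and dilute a true delay

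*Combined protocol and SAP*

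**What the plan says.** Section 3.3 (Secondary Study Endpoints) lists "Time to first intravenous opioid, oral opioid in PACU and after arrival to hospital room" and, as a separate item, "Time to oral-only opioids". The first item splits the time by route (intravenous, oral) and by place (PACU, hospital room). Neither item states when the clock starts, and no endpoint combines routes and places.

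On data, Section 6.2 says that an outcomes assessor surveys patients and that "Additional secondary outcomes will be pulled from the electronic medical record". On analysis, Section 7.2 says "A t-test will be used to compare the two arms of the study", followed by "We will apply other statistical methods as per Ochsner's statistics team & researchers". No censoring rule is given for a patient with no opioid of a given route or in a given place. Section 3.1 says "All patients will receive sedation with midazolam and/or fentanyl titrated to comfort during block procedures", and the plan does not say whether that fentanyl counts as a first intravenous opioid.

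The primary endpoint in Section 3.2 is "Cumulative opioid consumption (morphine equivalents) in the first 24 hours", a total that does not use these times.

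**The concern.** Time to first opioid is meant to show how long relief lasts before an opioid is needed. Once it is cut by place and route, each piece after the first depends on what came before it. An opioid given shortly before leaving PACU delays the next one, so a patient with early pain can show a long, apparently good, time in the room. An early oral dose can likewise put off or remove the first intravenous dose.

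If IPACK works early, fewer IPACK patients should need an opioid in PACU. The control arm's room times would then be lengthened more often by PACU doses, which pulls the arms together. The PACU piece sees only what happens before transfer. With no overall version, the pieces can disagree and no rule says which one answers the question. This problem arises even among patients who all received opioids, so it is distinct from the handling of patients who received none.

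**Working it through.** The documents give no expected time, event rate or power for this endpoint, so there is no stated figure to reproduce. The check has three parts, and every time value in it is an assumption.

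**1. Two patients.** Both reach the room 2 h after PACU arrival. A has an opioid at 0.5 h in PACU and the next at 6 h. B has none until 3 h.

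| Measure | A | B | Looks better |
|---|---|---|---|
| One clock from PACU arrival, any route and place | 0.5 h | 3.0 h | B |
| PACU component | 0.5 h | no event | B |
| Room component, clock starting at room arrival | 6 - 2 = 4.0 h | 3 - 2 = 1.0 h | A |
| Room component, clock starting at PACU arrival | 6.0 h | 3.0 h | A |

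The room component reverses the order under either clock, because what matters is that PACU doses are left out of it. By route: a patient given an oral opioid at 0.5 h and never an intravenous one has no intravenous event. That patient does better on time to first intravenous opioid than one whose first opioid is intravenous at 3 h.

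**2. How often patients are misordered.** Assumptions: time to first need exponential with mean 2, 4 or 8 h; PACU stay 1, 2 or 3 h; after each dose, a 3 h gap plus a new exponential time. Measured from room arrival, a patient treated in PACU has a longer room time than an untreated one with probability 0.58 to 0.85. Values above 0.5 mean that the component favours the treated patient.

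**3. Effect on the comparison of arms.** Assumptions: time from PACU arrival to first need is Weibull, with median 2 h (control) and 4 h (IPACK), so the true median delay is 4 - 2 = 2.0 h. Shape is 1, 1.5 or 2; PACU stay L is 1.5, 2 or 3 h; the redose interval is 3, 4 or 6 h and is the same in both arms. That gives 3 × 3 × 3 = 27 scenarios, with 400,000 simulated patients per arm in each. If the first need falls before L, doses repeat at the interval until one falls after L. Room time is that dose time minus L.

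- Difference in medians, IPACK minus control: -1.1 to +1.4 h. It is below 2.0 h in all 27 scenarios, below 1 h in 23 and negative in 4.
- All 4 reversals have a 6 h interval and a stay of 2 h or more. The PACU stay matters: at shape 2 with a 6 h interval the difference is about -1.1 h for stays of 2 h and 3 h, but about +1.4 h for 1.5 h.
- Difference in means, which is what a t-test compares: -0.67 to about +2.4 h, negative in 1 of 27. The true difference in means is 2.0 × Γ(1 + 1/shape) / (ln 2)^(1/shape), which is 2.89, 2.31 and 2.13 h for shapes 1, 1.5 and 2. The room difference is below its own true value in all 27.
- Since L is constant within a scenario, not subtracting it leaves these differences unchanged. They do not depend on where the clock starts.
- Share with no PACU event, exp(-ln 2 × (L/median)^shape): 21% to 68% of control patients and 60% to 91% of IPACK patients.

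**The case against.** A reader might infer that the endpoint restarts its clock on arrival in the room. The documents do not say so. The phrase about arrival can mark a new time zero or only the place where a dose is counted. Time zero is simply undefined, and the misordering in the room occurs on either reading.

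A reader might also infer that the room comparison would turn against IPACK. The scenarios do not support that as the expected result. Reversal of medians needs the longest assumed interval and a stay of 2 h or more, and means reverse once. The model also gives both arms the same redose interval, which assumes that IPACK does nothing after the first dose and so leans against it.

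Other points in the plan's favour stand. The PACU component of the same item scores the early-treated patient worse, and the 24-hour total counts that patient's dose. Times by place and route have descriptive value, and the item on oral-only opioids shows a genuine interest in route. This is one item in a list of eleven secondary endpoints, with no power claim attached.

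What these points do not supply is an overall time to first opioid. The PACU component cannot stand in for one, because under the assumed values it misses a large share of patients, more of them in the IPACK arm. Leaving the choice of clock, route and place until the data are seen would invite selective reporting.

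**Conclusion.** The concern holds for the room and single-route components. The split by route and place is explicit, time zero is undefined, and no overall version exists. That these components can favour a patient already treated follows from the definition alone. That they dilute a true delay was seen in all 27 assumed scenarios, where a median delay of 2.0 h appeared as -1.1 to +1.4 h. Reversal between arms is possible but confined to a few scenarios. None of the assumed times comes from the documents, so the figures show direction and plausible range and are not estimates for this trial. The consequence is limited to a secondary endpoint, but the definition is worth correcting before analysis because the correction is cheap.

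**What to change.** In Section 3.3, make the comparative endpoint the time from one stated origin (for example end of surgery or PACU arrival) to the first postoperative opioid of any route in any location. State that fentanyl given for the block procedure does not count. Censor patients with no opioid at a stated time, and name in Section 7.2 a time-to-event method such as the log-rank test. Keep the route- and location-specific times as descriptive summaries.

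The cost is protocol wording. The dose times should already be in the medication record, which Section 5.5 has investigators review, so no new data collection is expected. The small downside is that the route and location times lose comparative status.

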### **3.4 Primary Safety Endpoints**

Not applicable.

## **4 Subject Selection and Withdrawal**

### **4.1 Inclusion Criteria**

- Unilateral, primary tricompartment total knee arthroplasty
- Age 18 years or older
- ASA I-III
- Eligible for spinal or combined spinal epidural anesthetic
- Able to speak, read, and understand English
- Willing to participate in the trial

CONFIDENTIAL

This material is the property of Ochsner Clinic Foundation. Do not disclose or use except as authorized in writing by the study sponsor

## **4.2 Exclusion Criteria**

- Contraindication to regional anesthesia or peripheral nerve blocks
- Allergy to local anesthetics
- Allergy to NSAIDs
- Chronic renal insufficiency with Cr > 1.4 or GFR < 60
- Have chronic pain that is not related to their knee joint
- Have been using opioids on a chronic basis (daily or almost daily opioid use for 3 months or longer)
- Have a pre-existing peripheral neuropathy involving the operative site
- Body mass index greater than or equal to 40

## **4.3 Subject Recruitment and Screening**

All patients scheduled for primary unilateral TKA at Ochsner Medical Center Main Campus will be screened for eligibility. Eligible patients will be provided study information by one of the study investigators on day of surgery or in preoperative anesthesia clinic and given option to participate in the study. Participants will undergo written consent. There is no financial incentive for participation.

## **4.4 Early Withdrawal of Subjects**

### **4.4.1 When and How to Withdraw Subjects**

Patients may voluntarily withdraw at any time of the study. All procedures are performed preoperatively and further patient participation only includes questionnaires while admitted to the hospital. Patients may refuse to answer these questionnaires. Patients may also elect to discontinue their continuous ACB early.

### **4.4.2 Data Collection and Follow-up for Withdrawn Subjects**

All withdrawn subjects will be included in the intention to treat analysis. Already-accrued data for individuals who withdraw from the study will be maintained as part of the study data.

## **5 Study Drug**

### **5.1 Description**

Peripheral nerve blocks will be performed using preservative-free ropivacaine 0.25% with 1:300,000 epinephrine. Dilutions and sham subcutaneous injections will use preservative-free 0.9% saline. Package inserts are included as Attachment C.

### **5.2 Treatment Regimen**

Two treatment regimens exist: 1) continuous ACB and IPACK block both with ropivacaine 0.25% with 1:300,000 epinephrine; and 2) continuous ACB with ropivacaine 0.25% with 1:300,000 epinephrine and sham subcutaneous saline injection.

CONFIDENTIAL

This material is the property of Ochsner Clinic Foundation. Do not disclose or use except as authorized in writing by the study sponsor

### **5.3 Method for Assigning Subjects to Treatment Groups**

Subjects will be randomized to one treatment arm at time of trial enrollment. Randomization will be done using the website random.org's Coin Flipper, selecting the Susan B Anthony coin, and flipping 5 coins. Majority heads will be randomized to receive the IPACK block whereas majority tails will be randomized to receive the sham subcutaneous injection.

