A novel alternative to SNB is the infiltration of local anesthetic between the popliteal artery and capsule of the knee (IPACK) block that targets the terminal sensory nerve endings to the posterior knee joint. Common practice at our institution incorporates preoperative continuous ACB and single IPACK block. A retrospective review of patients at our institution who received IPACK block with continuous FNB compared to patients who received FNB alone showed similar VAS pain scores with significantly decreased narcotic requirements postoperatively. The same retrospective review showed that patients who received IPACK block with continuous ACB had clinically improved performance with physical therapy and a significantly shorter hospital stay. The goal of this study is to prospectively examine and hopefully confirm the observations of the retrospective chart review by studying the effect of preoperative IPACK

CONFIDENTIAL

This material is the property of Ochsner Clinic Foundation. Do not disclose or use except as authorized in writing by the study sponsor

block on opioid consumption, patient satisfaction, pain scores, walk distance, hospital length of stay, and several other secondary outcomes.

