### **5.5 Subject Compliance Monitoring**

Study investigators will ensure that correct multimodal therapy is ordered and review the medication record to ensure appropriate administration by nursing.

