#### **8.4 Unblinding Procedures**

Physicians performing the study intervention will not be blinded to the drug or technique. The study participants, outcome assessors/researchers, other anesthesia personnel, surgeons, physician assistants, and nurses will be blinded to the treatment arm. Unblinding will occur at the conclusion of the study in order to facilitate group analysis.

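### The coin flip is set at enrolment with no named operator and no requirement to keep its output, so the plan does not secure its own rule that only the block anesthesiologist knows the arm

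*Combined protocol and SAP*

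**What the plan says.** Section 5.3 fixes the timing: "Subjects will be randomized to one treatment arm at time of trial enrollment". The method is the random.org coin flipper with five coins: "Majority heads will be randomized to receive the IPACK block whereas majority tails will be randomized to receive the sham subcutaneous injection". Section 3.1 describes the same method but gives no time point. It says only that patients are recruited, consent in writing and are then randomized.

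Under Section 3.1, patients are "recruited either on day of surgery or in the preoperative anesthesia clinic by one of the study investigators"; Section 4.3 repeats this. On concealment, Section 3.1 says: "Only the regional anesthesiologist performing the block will know the randomization status". Sections 3.1 and 8.4 list those who must not know the arm. The list includes the outcome assessors and researchers, and "other anesthesia personnel, surgeons, physician assistants, and nurses will be blinded to the treatment arm".

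Attachment A is offered as an example of the website. Its sample result page carries a timestamp, but no section says that such pages are to be saved or linked to a subject number.

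**The concern.** The timing rule and the concealment rule do not fit together for every patient. If a patient enrols in clinic and is randomized there, someone must make the flip and see the result, and the plan does not say who. The person known to be present is the recruiting investigator, who may not be the anesthesiologist who later performs the block.

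Two things are at stake:

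- **Selection.** The website can be used again at will. Someone who sees an unwanted result could flip again, or could let the patient drop out. This biases the comparison only if the action is related to prognosis. A preference is conceivable, since Section 1.1 says: "Common practice at our institution incorporates preoperative continuous ACB and single IPACK block". The documents do not state that anyone holds one.
- **Blinding.** If the recruiting investigator makes the flip, a researcher who is meant to be blinded knows the arm from enrolment onward.

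**Working it through.** **1. The plan's own allocation rule.** P(at least 3 heads in 5 fair coins) = (10 + 5 + 1)/32 = 0.5. Expected arm size is 72 × 0.5 = 36, which agrees with the roughly 36 per arm in Section 7.1. Each flip is independent, so no assignment can be predicted from earlier ones. The generator is sound.

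**2. The provisions side by side.**

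| Question | What the protocol gives |
|---|---|
| When is the flip made? | At enrolment (5.3); no time point (3.1) |
| When and by whom are patients recruited? | Clinic or day of surgery, by a study investigator (3.1, 4.3) |
| Who makes the flip? | Not stated |
| Who may know the arm? | Only the anesthesiologist performing the block (3.1) |
| Who prepares the injection? | Any regional anesthesia team member (5.4) |
| Is the flip output kept? | Not stated; sample page only (Attachment A) |

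For enrolment on the day of surgery the rows can be reconciled. For clinic enrolment they need a step that the plan does not supply.

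**3. How much bias could repeated flips cause?** The documents give no rates, so all three inputs here are assumptions:

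- half of the 72 patients (36) are steered toward IPACK;
- a share q of their sham results is re-flipped once;
- these patients differ from the rest by 0.5 SD in expected opioid use.

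Formulas:

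- P(IPACK) for a steered patient: p1 = 0.5 + 0.25q. For the others, p0 = 0.5.
- Expected re-flips: 36 × 0.5 × q.
- Difference between arms in the share of steered patients: D = p1/(p1 + p0) − (1 − p1)/[(1 − p1) + (1 − p0)].
- Bias: 0.5 SD × D.

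| q | Expected re-flips | p1 | D | Bias (SD) | P(flagged by arm counts) |
|---|---|---|---|---|---|
| 0.1 | 1.8 | 0.525 | 0.025 | 0.0125 | 0.049 |
| 0.2 | 3.6 | 0.550 | 0.050 | 0.025 | 0.063 |
| 0.5 | 9 | 0.625 | 0.127 | 0.063 | 0.170 |
| 1 | 18 | 0.750 | 0.267 | 0.133 | 0.554 |

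The last column is an exact two-sided binomial test on the number assigned to IPACK. It rejects at 27 or fewer, or at 45 or more, and its actual level is 0.044. Arm counts would therefore usually miss the problem. A prognostic difference of 0.25 SD halves the bias and 1 SD doubles it. Its direction follows the sign of that difference. If all patients were re-flipped at the same rate regardless of prognosis, the expected bias would be zero.

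**4. Why the bias stays in SD units.** Section 7.1 quotes an effect size of 0.4 and 64 patients. With n per arm = 2(1.96 + 0.84)²/d², a two-sided 5% test and 80% power, d = 0.4 needs 99 per arm (198 in total). A total of 64 (32 per arm) corresponds to d of about 0.71. The unit of 0.4 is therefore unclear, and it is not a safe yardstick for a bias in SD.

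**The case against.** The case on the other side is substantial, and much of it stands.

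- **The block anesthesiologist is the natural operator.** Making that person the flipper satisfies Section 3.1 as written, and on the day of surgery enrolment and block may fall close together. A reader might infer that the concealment rule has no mechanism at all. The text does not support that: the operator is left implicit, and the timing conflict is confined to clinic enrolment. What remains is that no section names the operator.
- **Re-flipping is not permitted.** Section 5.3 prescribes one set of five coins with the majority deciding, so a second set would already be a departure. Silence on a binding first result does not authorise repeats. It does leave them hard to see.
- **Some record is presupposed.** Section 8.4 unblinds at study end for the group analysis, which needs a stored assignment, and Section 9.2 defines source data as whatever is needed to reconstruct the trial. A reader might infer that no allocation record would exist; that goes too far. What is missing is a requirement to keep the flip output. A record of the final arm alone would not show a repeat.
- **There are partial safeguards.** Section 3.1 says: "Consecutive patients who meet preset inclusion and exclusion criteria will be recruited". Section 4.4.2 keeps withdrawn subjects in the intention-to-treat analysis, Section 11 requires consent before any study procedure, and Section 10.2 permits audits. These make a dropped patient easier to trace. They do not reveal a repeated flip.
- **The investigators' medication check.** Section 5.5 says: "Study investigators will ensure that correct multimodal therapy is ordered and review the medication record to ensure appropriate administration by nursing". A reader might infer that an unblinded recruiter could shift opioid use, the primary endpoint, by this route. The documents do not show it. The check concerns the multimodal regimen listed in Section 3.1, not opioid titration; nurses are to be blinded; and it is not established that the recruiter makes the flip.

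**Conclusion.** The point holds in a limited form. The enrolment timing in Section 5.3, combined with clinic recruitment by a study investigator, does not secure the concealment stated in Sections 3.1 and 8.4. No section in the text available for review names who flips or requires the output to be kept. The fairness of the coin rule is not in question.

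The likely bias is small: 0.01 to 0.13 SD for q from 0.1 to 1, in either direction, given the assumed steering of half the patients and a 0.5 SD prognostic difference. The upper end requires every unwanted result in the steered half to be re-flipped, and nothing in the documents suggests that this is intended or expected. A reader might go on to express the bias as a percentage of the 0.4 in Section 7.1. That is not supported, because the unit of 0.4 is unclear.

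This should be corrected because the remedy is cheap and makes the plan's own blinding rule workable. It is not evidence that the comparison will be biased.

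**What to change.** In Section 5.3 replace the enrolment timing with the following, and add the same text to Section 3.1:

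> On the day of surgery, after written consent and confirmed eligibility and immediately before the block, the regional anesthesiologist performing the block enters the subject number and time in an allocation log and makes one set of five flips. The first result is binding, and the timestamped output is filed with the subject number. The assignment is available only to that anesthesiologist and to any regional team member who must prepare the injection. Outcome assessors and other investigators do not see the log until the study ends.

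The allowance for the team member who prepares the injection is needed for consistency with Section 5.4. Where practicable, the block performer should not be the person who recruited that patient.

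An acceptable alternative is a concealed computer-generated sequence, held by the institution's statisticians and opened once per patient at the same time point. It would close the re-flip gap but must be protected against leaks.

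The cost is a short amendment plus one log line and one saved page per patient (72 of each), with no extra patients or visits. Separating recruiter and block performer may need some rostering. A filed timestamp does not fully exclude an earlier flip; logging the time before flipping narrows that gap.
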